6.1 Rationale for study

In order to improve RAASi treatment in terms of increasing the proportion of patients who achieve target doses according to clinical guidelines, the maximum tolerated doses that are currently achieved need to be determined. This study will therefore describe the characteristics of patients with CKD (and at least one of the following: HF and/or T2DM)

who are treated with RAASi but do not achieve target dose. The maximum tolerated doses achieved by these patients and the length of time on these doses will be reported.

7. Aim and objectives

7.1 Aim

To investigate the use of RAASi in the real world UK NHS setting in patients with CKD stage 3 or 4 and who also have HF and/or T2DM.

7.2 Primary objective

1. To describe doses of RAASi prescribed to patients with CKD in the UK NHS setting

7.3 Secondary objectives

1. To describe doses of MRA prescribed to patients with CKD and HF
2. To describe other drug types concomitantly prescribed for CKD and/or HF in patients treated with RAASi
3. To describe clinical outcomes associated with RAASi treatment
4. To describe the demographic and clinical characteristics of patients treated with RAASi who do not achieve target dose, at initiation of treatment

8. Hypothesis

This is a descriptive study and therefore an a priori hypothesis will not be tested.

9. Study design and methodology

The study is designed and will be conducted according to the requirements of the European Network of Centres for Pharmacoepidemiology and Pharmacovigilance (ENCePP) and International Society for Pharmacoepidemiology (ISPE) guidance, as appropriate^{10,11}. This will be a multi-centre, retrospective non-interventional study of patients with CKD and HF

and/or T2DM. The study will take place in between five and ten NHS secondary care centres in the UK.

9.1 Study time periods

Data will be collected retrospectively over 24 months, from 01 January 2016 to 31 December 2017. Patients who were initiated on RAASi between 01 January 2016 and 31 December 2016 will be retrospectively followed up for 12 months from the date of RAASi initiation (study index date), i.e. their first prescription of RAASi during the enrolment period.

9.2 Study population

The study will include adult patients with CKD stage 3 or 4 who do not achieve target dose of RAASi and have at least one of the following:

- heart failure (HF)
- type 2 diabetes mellitus (T2DM)

Where:

- CKD stage 3 or 4 is defined as estimated glomerular filtration rate (eGFR) $>14\text{ml}/\text{min}/1.73\text{m}^2$ and $<60\text{ml}/\text{min}/1.73\text{m}^2$
- HF is defined as presence of reduced ejection fraction and left ventricular ejection fraction (LVEF) $<40\%$
- T2DM is defined as a confirmed diagnosis in medical records
- Target dose is defined as recorded in medical records, or Summary of Product Characteristics (SPC) if not recorded in medical records (see Appendices)

9.2.1 Inclusion criteria

- Diagnosed with CKD stage 3 or 4 and at least one of the following: HF and/or T2DM
- Prescribed a RAASi for the first time at an outpatient CKD and/or HF clinic between 01 January 2016 to 31 December 2016 ('the enrolment period')
- Aged ≥ 18 years when prescribed a RAASi for the first time during the enrolment period

- Patients who do not achieve target dose of RAASi during the observation period
- With ≥ 12 months follow up data during the observation period
- Consent to researcher access to their medical records for study data extraction (living patients only)

9.2.2 Exclusion criteria

- Received heart or kidney transplant before or during the observation period
- Diagnosed with type 1 diabetes mellitus or acute kidney injury
- Diagnosed with metastatic, late-stage or end-stage cancer with < 12 months life expectancy
- Hospital medical records are unavailable for review
- Enrolled in a blinded clinical trial of an investigational medicinal product during the observation period

9.2.3 Participant recruitment

The NHS clinical care team will identify eligible patients and seek consent from each living patient for their hospital and primary care medical records to be used in the study. Data from patients who are deceased will only be collected by the NHS care team preserve patient confidentiality. The NHS care team will contact living patients by post or face to face at the patients' next hospital appointment. Consecutive patients will be selected by the NHS care team in reverse chronological order of RAASi initiation (index date).

9.3 Data collection

Data from patients' medical records will be collected by members of the NHS care team or external pH Associates researchers using electronic data collection forms (eCRFs) within an electronic data capture (EDC) system called MACRO. This is a web-based, secure data capture and data management tool.

Patients will be identified in all study records by a unique study code to preserve patient confidentiality. Clinical data from secondary care medical records will be collected either by pH Associates or the NHS care team. Information provided by primary care on patients'

RAASi and concomitant drug use for CKD and/or HF, as well as haematology and biochemistry test results, during the observation period will be extracted from patient records within secondary care.

There will be no change to the clinical management of patients as a result of taking part in the study. No additional patient investigations or tests will be required.

9.4 Data sources

Data will be extracted from medical records in secondary care. This will include:

- Patient demographic and clinical data recorded in the electronic Patient Administration System (PAS), service databases and medical notes, prescribing records, laboratory reports and investigation reports.
- CKD/HF prescribing information and haematology and biochemistry test results from primary care (where available within patients' secondary care records).

9.5 Study endpoints and variables

Results will be presented by RAASi drug type, i.e. angiotensin-converting enzyme (ACE) inhibitors and angiotensin II receptor blockers (ARBs), and patient group (CKD and HF, CKD and T2DM, CKD and HF and T2DM), where appropriate. Patient-level data will be collected from each centre for the following endpoints during the observation period.

9.5.1 Primary endpoint

The primary endpoint of this study is the mean maximum tolerated daily dose of RAASi achieved (as percentage of target dose).

9.5.2 Secondary endpoints

The following endpoints will also be measured:

Prescribing modalities, including concomitant prescribing

- Length of time on maximum tolerated daily dose of RAASi
- Proportion of patients with HF who receive RAASi and MRA

- Maximum tolerated daily dose of MRA achieved in patients with HF
- Length of time on maximum tolerated daily dose of MRA in patients with HF
- Distribution of other drugs concomitantly prescribed for CKD and/or HF in patients treated with RAASi, by drug type

Clinical outcomes

- Proportion of patients with elevated serum potassium level (>5.1 mmol/L, >5.5 mmol/L or >6.0 mmol/L) during the observation period
- Number of episodes per patient with elevated serum potassium level (>5.1 mmol/L, >5.5 mmol/L or >6.0 mmol/L)
- Change in mean serum potassium level (from index date to last result during observation period)
- Change in mean serum creatinine level (from index date to last result during observation period)
- Change in mean urine protein level (from index date to last result during observation period)
- Change in mean blood pressure level (from index date to last result during observation period)
- Proportion of patients who stop RAASi treatment at least once during the observation period
- Reason(s) for changing RAASi dose or stopping RAASi treatment, where relevant

The following patient characteristics will also be included in analyses:

- Age at index event
- Sex
- Ethnicity
- HF status
- Comorbidities documented at baseline
- Length of time since diagnosis of CKD (and HF and/or T2DM, if relevant) at index event
- eGFR at baseline

- LVEF at baseline, if diagnosed with HF

9.5.3 Variables to be collected

The variables to be collected in this study are shown in Table 2.

Table 2 Study variables

Data Item	Required detail	Time point(s)	Data source(s)
Date of birth	MM/YYYY	Index event	Hospital medical record
Gender	F, M	Index event	Hospital medical record
Ethnicity	Based on categories recommended by Office for National Statistics: White, Mixed / Multiple ethnic groups, Asian / Asian British, Black / African / Caribbean / Black British, Other ethnic group	Baseline	Hospital medical record
Date of CKD diagnosis	MM/YYYY	Baseline	Hospital medical record
Date of HF diagnosis, if relevant	MM/YYYY	Baseline	Hospital medical record
Date of T2DM diagnosis, if relevant	MM/YYYY	Baseline	Hospital medical record
Comorbidities	Based on diseases and conditions recorded in medical record	Baseline	Hospital medical record
eGFR	Date of observation, rate	Baseline until end of	Hospital medical records,

		observation period	including primary care correspondence
LVEF	Date of observation, ejection fraction	Baseline until end of observation period	Hospital medical records, including primary care correspondence
Serum potassium	Date of observation, level	Index date until end of observation period	Hospital medical records, including primary care correspondence
Serum creatinine	Date of observation, level	Index date until end of observation period	Hospital medical records, including primary care correspondence
Urine protein (albumin:creatinine ratio, ACR or protein:creatinine ratio, PCR)	Date of observation, level, type of test	Index date until end of observation period	Hospital medical records, including primary care correspondence
Blood pressure	Date of observation, level	Index date until end of observation period	Hospital medical records, including primary care correspondence
RAASi prescriptions	Drug name, dose, start date	Index date until end of observation	Hospital medical records, including

		period	primary care correspondence
MRA prescriptions, if relevant	Drug name, dose, start date	Index date until end of observation period	Hospital medical records, including primary care correspondence
Concomitant medications for CKD and/or HF	Drug name, start date	Index date until end of observation period	Hospital medical records, including primary care correspondence
Change in RAASi treatment	Date of change, reason for dose change/stopping of treatment	Index date until end of observation period	Hospital medical records, including primary care correspondence

10. Data management and quality control

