Maximum tolerated dose: highest dose of RAASi (or MRA) recorded in medical records during observation period

Observation period: the 12 month period from index event

Target dose: as stated in medical records, national or international clinical guidelines or Summary of Product Characteristics (SPC) if not recorded in medical records (see Appendices)

Type 2 diabetes (T2DM): Chronic metabolic disorder that results in hyperglycaemia (high blood glucose levels) due to the body's inability to produce enough insulin or lack of ability to utilise the insulin being produced (insulin resistance). Confirmed diagnosis in medical records

4. Study synopsis

Title	
SoMoR – UK (Study of Management of RAASi in UK)
 
A multi-centre, retrospective observational study on renin-angiotensin-aldosterone system inhibitors (RAASi) management in patients treated for chronic kidney disease alongside heart failure and/or type 2 diabetes mellitus.

Background and rationale for study	
In order to improve renin-angiotensin-aldosterone system inhibitors (RAASi) treatment by increasing the proportion of patients who achieve target doses according to clinical guidelines, the maximum tolerated doses that are currently achieved need to be determined. This study will therefore describe the characteristics and treatment outcomes of patients with CKD and at least one of the following: heart failure (HF) and/or type 2 diabetes mellitus (T2DM) and who receive RAASi in the real world UK NHS setting but do not achieve target dose. The maximum tolerated doses achieved by these patients and the length of time on these doses will be reported.

Objectives	
Primary objective
 
 1. To describe doses of RAASi prescribed to patients with CKD in the UK NHS setting 
Secondary objectives
 
 1. To describe doses of mineralocorticoid receptor antagonist (MRA) prescribed to patients with CKD and HF 2. To describe other drug types concomitantly prescribed for CKD and/or HF in patients treated with RAASi 3. To describe clinical outcomes associated with RAASi treatment 4. To describe the demographic and clinical characteristics of patients treated with RAASi and do not achieve target dose, at initiation of treatment
Hypothesis statement	
This is a descriptive study and therefore an a priori hypothesis will not be tested.

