10.2 Data quality checks

Data collection will be completed by trained staff either from pH Associates or the NHS care team at study centres. All data collectors will be provided with Data Collection Guidelines to support consistent completion of eDCFs. Additionally, the same data collector will be used at each centre, wherever possible. Data entered into eDCFs will be validated at the point of entry into MACRO using criteria to be pre-agreed criteria with Vifor Fresenius Medical Care Renal Pharma UK Ltd before the start of data collection. All data received by pH Associates will be checked for participant eligibility, accuracy and completeness using programmed validation checks, in accordance with the agreed data management plan.

Furthermore, the accuracy and quality of data collection will be monitored by the completion of source data verification (SDV) for 10% of eDCFs at each centre by pH Associates staff. SDV will only be possible for secondary care data. SDV will not be conducted for primary care prescribing and test results data as access to source GP records will not be sought. Where data collection is completed by pH Associates staff, the staff member who carries out the SDV will be different to the person responsible for data collection at that specific centre. Remedial training will be given to data collectors if necessary.

Quantitative data collected for laboratory (haematology and biochemistry) parameters will be standardised per centre using laboratory reference ranges entered on the eDCF. This will allow pooling of these study parameters across centres. Data submitted to the study will be checked for completeness and queries will be raised by the pH Associates data management

team. Study centres will be required to co-operate with the data management team in the resolution of these queries. Where data queries are raised by the pH Associates data management team, study centres will be required to cooperate with pH Associates in the resolution of these queries. On completion of the first three eDCFs from at least two centres, a pilot of the data collection process will be completed. This will assess the feasibility of capturing the study dataset using the eDCF, confirm that data collection can be achieved efficiently, and also establish that the data collection method is suitably robust.

11. Study sample size

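### The patient's recorded target dose decides eligibility and is the primary endpoint's denominator, but Table 2 has no field for that target or its source

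*Protocol*

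**What the plan says.** Two places in the protocol define the target dose, and both put the patient's record first. Section 3: "Target dose: as stated in medical records, national or international clinical guidelines or Summary of Product Characteristics (SPC) if not recorded in medical records". Section 9.2: "Target dose is defined as recorded in medical records, or Summary of Product Characteristics (SPC) if not recorded in medical records". They differ on the fallback, since only Section 3 names guidelines.

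The target is then used twice.

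- **Eligibility.** Section 9.2.1 includes "Patients who do not achieve target dose of RAASi during the observation period". Under 9.2.3 the judgement is made at the centre: "The NHS clinical care team will identify eligible patients and seek consent from each living patient".
- **Primary endpoint.** Section 9.5.1 expresses each patient's highest tolerated daily RAASi dose as a percentage of the target and takes the mean.

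Section 9.5.3 introduces the data list with "The variables to be collected in this study are shown in Table 2". The RAASi prescription row asks for drug name, dose and start date. The row on changes asks for the date and the reason. No other row concerns the target.

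Section 10.2 adds a central safeguard: "All data received by pH Associates will be checked for participant eligibility, accuracy and completeness using programmed validation checks". Section 12 gives the analysis to the same organisation.

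**The concern.** A percentage of target needs two numbers per patient, and Table 2 lists only the dose. Where the record states its own target, the centre can judge eligibility against that figure. An analyst working from the listed variables would have only a published figure, found by drug name. The two steps could then rest on different targets for the same patient.

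Two things are at stake. The primary mean would not be the quantity defined in 9.5.1 for those patients. And a programmed check run on a published figure could err both ways. It would pass a patient who had reached a lower recorded target and should not be in the study, and it would flag a properly enrolled patient whose recorded target is above the published one.

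This differs from an analysis detail that can wait for the SAP. An SAP can say how to use a target dose, but it cannot supply a patient-level value that was not collected.

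**Working it through.** The plan states no figure on this point, so there is none to reproduce. The check is a comparison of passages, followed by arithmetic on assumed inputs.

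**1. What the definition needs and what Table 2 lists**

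| Needed | In Table 2? |
|---|---|
| Highest RAASi dose in the observation period | Yes (drug, dose, start date) |
| Target stated in the record | No |
| Source of the target applied (record, guideline or SPC) | No |
| Published target, if the record states none | Not collected, but can be looked up by drug |

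The gap therefore concerns patients with a recorded target. It changes a result only where that target differs from the published one.

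**2. The lookup is not always a single number**

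Appendix 1 gives ranges for two drugs and no target for eprosartan.

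- Lisinopril, 20–35 mg daily: a dose of 20 mg is 20/20 = 100% or 20/35 = 57.1% of target.
- Enalapril, 10–20 mg twice daily, or 20–40 mg per day: a dose of 20 mg per day is 20/20 = 100% or 20/40 = 50%.

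So even under the fallback, the database would not show which figure the centre applied.

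**3. Size if recorded targets are lower**

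All inputs here are assumptions; the documents give none.

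- Patients without a recorded target have a highest dose of 25, 50, 75 or 100% of the published figure in 35, 35, 10 and 20% of cases.
- A share s has a recorded target at half the published figure, and these patients sit equally at 25% and 50% of the published figure.

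Among those without a recorded target, 0.80 are eligible, contributing 0.35×25 + 0.35×50 + 0.10×75 = 33.75. Among those with one, half are eligible: they are at 25% of the published figure, which is 50% of their own target. The eligible fraction is 0.8(1−s) + 0.5s = 0.8 − 0.3s.

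- Mean as defined = [33.75(1−s) + 0.5s×50] / (0.8 − 0.3s)
- Mean with published denominator = [33.75(1−s) + 0.5s×25] / (0.8 − 0.3s)
- Gap = 12.5s / (0.8 − 0.3s)

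| s | As defined | Published denominator | Gap (points) |
|---|---|---|---|
| 10% | 42.69 | 41.07 | 1.6 |
| 20% | 43.24 | 39.86 | 3.4 |
| 30% | 43.84 | 38.56 | 5.3 |
| 40% | 44.49 | 37.13 | 7.4 |

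For scale, Table 3 at a mean of 40% and 100 patients runs from 36% to 44%, a half-width of 4 points. The gap reaches 4 when 12.5s = 4(0.8 − 0.3s), so s = 3.2/13.7, about 23%.

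**4. The direction can reverse**

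Assume a mean of 60% of the recorded target, and a share f whose recorded target is k times the published one. The mean on the published denominator is 60(1−f) + 60kf.

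| f | k = 0.5 | k = 0.75 | k = 1.5 |
|---|---|---|---|
| 10% | 57.0 | 58.5 | 63.0 |
| 25% | 52.5 | 56.2 | 67.5 |
| 50% | 45.0 | 52.5 | 75.0 |

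Table 3 gives 56% to 64% for a mean of 60% with 100 patients. A mixture of lower and higher recorded targets would partly cancel.

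**The case against.** The strongest reply is that Table 2 may not be everything on the electronic form. Section 10.2 has laboratory reference ranges entered on the eDCF, yet Table 2 has no such row. Table 2 also has no specific row for transplant or trial enrolment, although eligibility is to be checked centrally. The eDCF and the Data Collection Guidelines are not shown. The synopsis and Sections 9.3 and 10.2 also let the contracted organisation's researchers extract from the records, so at some centres they would see a recorded target. This stands. A reader might infer that the figure never reaches the database, or that the analyst is bound to use Appendix 1, but no passage says either. What remains is that the protocol's own list of variables omits the target, whoever does the extraction.

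A reader might also infer that the primary endpoint cannot be computed at all. That goes too far. Where the record states no target, the definition itself points to published sources, and drug and dose are collected.

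Two further consequences should not be put down to the missing row. Excluding someone who reached a lower recorded target, and the tension with Section 6.1, which speaks of targets in clinical guidelines, both follow from putting the record first. A new field would change neither. Likewise, an enrolled patient scoring 100% or more against the published figure requires a recorded target above it. That is possible, but the illustration with halved targets contains no such patient.

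Finally, the size rests on chosen inputs. In the halved-target illustration every error runs one way, and below a share of about 23% the gap is smaller than Table 3's 4 points.

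**Conclusion.** The point holds in a limited form. The protocol defines the target as the recorded one first and uses it for both eligibility and the primary denominator, but lists no variable that captures it. Followed as written, the primary percentage and the eligibility check cannot be produced as defined for patients whose recorded target differs from the published one.

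The number of such patients is unknown, and so are the size and sign of the effect. The range of 1.6 to 7.4 points assumes shares of 10% to 40%, all with targets at half the published figure, and the dose mix given above. It is an illustration and does not estimate bias in this study. Without the field, the sponsor could not determine the effect from the listed data.

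**What to change.** - Add to Table 2 and the eDCF, for each RAASi drug prescribed, the target dose used for the eligibility decision and its source (record, guideline or SPC). It has to be per drug because targets are drug-specific and patients may switch within the 12 months.
- Use that same value as the denominator of the primary percentage and in the programmed check that each enrolled patient's highest dose is below target.
- Report, as a sensitivity column, the percentage against one published reference for every patient.
- The sponsor should reconcile the target-dose wording in Section 3, 9.2, 6.1 and Appendix 1. This includes the fallback source (9.2 names the SPC; Appendix 1 cites a cardiology guideline and the British National Formulary), the two ranges and the missing eprosartan entry. No view is taken here on which target is right.

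The cost is one extra field per drug and one extra table column. The centre already has to identify the target to judge eligibility.

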16.1 Protection of human subjects	30

17.	Study timelines	31
18.	Administrative and legal obligations	31
18.1	Study amendments and study termination	31
18.2	Study documentation and archive	31
18.3	Ethical and regulatory approvals	32
18.4	Ethical issues	32
19.	Communication of study results	32
20.	Study support.....	33
21.	References	34
22.	Appendices.....	36

1. List of tables

Table 1. Study amendments	14
Table 2 Study variables	21
Table 3 Confidence limits for different sample sizes and mean doses of RAASi achieved	25
Table 4 study timelines	31

2. List of abbreviations

Abbreviation	Definition
ACEi	Angiotensin converting enzyme inhibitor
ACR	albumin:creatinine ratio
AE	Adverse event
ADR	Adverse drug reaction
ARB	Angiotensin receptor blocker
CI	Chief Investigator
95% CI	95% confidence interval
CKD	Chronic kidney disease
EDC	Electronic data capture
eDCF	Electronic data collection form
eGFR	Estimated glomerular filtration rate
ENCePP	European Network of Centres for Pharmacoepidemiology and Pharmacovigilance
GAfREC	Governance Arrangements for Research Ethics Committees
GCP	Good Clinical Practice
GP	General Practitioner
HF	Heart failure
HRA	Health Research Authority
ISPE	International Society for Pharmacoepidemiology
LVEF	Left ventricular ejection fraction
MHRA	Medicines and Healthcare Products Regulatory Agency
MRA	Mineralocorticoid receptor antagonist
NIHR	National Institute for Health Research
NHS	National Health Service
PAS	Patient Administration System
PCR	protein:creatinine ratio
PI	Principal investigator

Abbreviation	Definition
R&D	Research and Development
RAASi	Renin–angiotensin–aldosterone system inhibitors
REC	Research Ethics Committee
SADR	Serious adverse drug reaction
SDV	Source data verification
STROBE	Strengthening the Reporting of OBservational Studies in Epidemiology
T2DM	Type 2 diabetes mellitus
UK	United Kingdom

3. List of definitions

Baseline: test result in medical records with date closest to and before the index event and within 12 months of the index event, or on the same date as the index event

Chronic Kidney Disease (CKD) stages 3 and 4: estimated glomerular filtration rate (eGFR) $>14\text{ml}/\text{min}/1.73\text{m}^2$ and $<60\text{ml}/\text{min}/1.73\text{m}^2$

Enrolment period: the 12 month period between 01 January 2016 and 31 December 2016

Heart failure (HF): presence of reduced ejection fraction and left ventricular ejection fraction (LVEF) $<40\%$

Index event: first prescription of RAASi during the enrolment period

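### A pre-treatment starting value is not assured for the four secondary change endpoints, because Table 2 collects those variables only from the index date

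*Protocol*

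**What the plan says.** The Section 3 definition of baseline has two parts. The first is a "test result in medical records with date closest to and before the index event and within 12 months of the index event". The second admits a result "or on the same date as the index event".

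Table 2 (Section 9.5.3) uses two windows for repeated measurements. For eGFR and LVEF it is "Baseline until end of observation period". For serum potassium, serum creatinine, urine protein and blood pressure it is "Index date until end of observation period".

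Section 9.5.2 sets the potassium endpoint as "Change in mean serum potassium level (from index date to last result during observation period"). The creatinine, urine protein and blood pressure endpoints follow the same pattern. They are numbers 9 to 12 in the synopsis.

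Section 9.1 states: "Data will be collected retrospectively over 24 months, from 01 January 2016 to 31 December 2017".

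On treatment start, Section 3 makes the index event the "first prescription of RAASi during the enrolment period". Section 9.1 equates the two ideas: "date of RAASi initiation (study index date), i.e. their first prescription of RAASi during the enrolment period". The inclusion criterion in Section 9.2.1 asks for a first-time RAASi prescription at an outpatient CKD or HF clinic in 2016. Table 2 collects RAASi prescriptions from the index date only.

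Section 12 plans paired tests for within-group differences. Section 12.1 restricts each analysis to patients with data and rules out any statistical handling of missing values.

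**The concern.** A change endpoint is only as good as its starting value. The protocol has a sensible baseline definition and uses it for two variables, neither of which has a change endpoint. The four variables that do have one are collected without a look-back. The only value at or before treatment start that the database can hold for them is one dated on the day of the index prescription.

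Two things are at stake: the number of patients who can enter each paired analysis, and what the change means if a later, on-treatment result stands in for the missing start. Part of any early movement in potassium or creatinine after starting a RAASi would then already be in the starting value.

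This cannot be left to the statistical analysis plan. That plan can choose among collected results, but it cannot analyse results that were never extracted. By Section 12 it is due only before data collection is completed, and Table 4 places collection in March to July 2018.

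**Working it through.** The protocol gives no figure on this point. Table 3 concerns the precision of the mean RAASi dose only. The check is therefore a comparison of sections, followed by an illustration under stated assumptions.

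**Step 1: possible meanings of a change that starts at the index date.**

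- The Section 3 baseline: results before the index date are needed, but Table 2 does not collect them for these variables.
- A same-day result: patients without one have no pair and leave the analysis under Section 12.1.
- The first result after the index date: the patient stays in, but the starting value is on treatment.

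The protocol does not say which applies. None of the three gives every patient a pre-treatment start.

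**Step 2: loss of precision if only same-day results are used.** Let s be the share of patients with a same-day result. The protocol does not give s, so 0.2 to 0.8 is an assumed range. With n = 100 planned (Section 11) and an unchanged standard deviation, the usable number is 100 × s and the interval widens by √(1/s).

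| s | usable n | widening |
|---|---|---|
| 0.2 | 20 | √5 = 2.24 |
| 0.5 | 50 | √2 = 1.41 |
| 0.8 | 80 | √1.25 = 1.12 |

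The comparator of 100 assumes that every patient has both a start and a last result, so it is a best case.

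**Step 3: attenuation if the first later result fills the gap.** Let f be the share of the treatment effect already present at that result (also assumed). Same-day results are taken as pre-dose, and the true mean change as equal in both groups of patients. Then observed change ÷ true change = s + (1 − s)(1 − f) = 1 − (1 − s)f.

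| s | f = 0.5 | f = 0.8 |
|---|---|---|
| 0.2 | 1 − 0.8 × 0.5 = 0.60 | 1 − 0.8 × 0.8 = 0.36 |
| 0.5 | 1 − 0.5 × 0.5 = 0.75 | 1 − 0.5 × 0.8 = 0.60 |
| 0.8 | 1 − 0.2 × 0.5 = 0.90 | 1 − 0.2 × 0.8 = 0.84 |

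At s = 1, with no earlier RAASi use, there is neither loss nor attenuation.

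**Step 4: the collection window.** A 12-month look-back from any index date in 2016 before 31 December starts in 2015, while Section 9.1 opens collection on 01 January 2016. Read literally, the two conflict, and this touches the existing eGFR and LVEF baselines too.

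**Step 5: treatment start.** A first prescription within 2016, a first prescription at an outpatient clinic, and initiation coincide only if the patient had no earlier RAASi from another source. No exclusion criterion in Section 9.2.2 addresses earlier use, and prescriptions before the index date are not collected. The database cannot show which patients were new users.

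**The case against.** A reader might infer that the four endpoints have no pre-treatment baseline at all. The documents do not support that. Same-day results count as baseline under Section 3 and are collected. The index event is an outpatient clinic prescription, so same-day values are plausible, above all for blood pressure. The baseline is not assured, which is different from absent.

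A reader might also infer that long-term RAASi users are in the sample and distort the primary dose endpoint. Several sections point the other way: the synopsis and Section 9.1 speak of initiation, Section 9.2.1 asks for a first-time prescription, the care team identifies patients, and Section 10.2 provides eligibility checks. What remains is an ambiguity between sections and the absence of a field to resolve it.

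On Section 9.1, it can fairly be said that the 24 months simply describe enrolment plus follow-up. Table 2 asks for diagnosis dates that may lie before 2016, so an absolute bar on earlier entries is not a sensible reading. Nor would it be right to say that half of the look-back is lost. Section 9.2.3 selects patients in reverse chronological order of index date, which favours late-2016 dates, and only the closest prior result matters. A wording clarification is all that stands.

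Finally, baseline eGFR gives a pre-index view of renal function. That softens the creatinine gap but does nothing for potassium, urine protein or blood pressure.

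**Conclusion.** The point holds in limited form: for endpoints 9 to 12 a pre-treatment start exists only for patients with a same-day, pre-dose result and no earlier RAASi use. The others are either lost or measured from an on-treatment value, probably biasing the change toward zero.

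The size is unknown. The widening of 2.24 to 1.12 times rests on an assumed 20% to 80% same-day availability; the attenuation figures also need an assumed f. Neither range is evidence about this study, and availability may well differ between blood pressure and urine protein.

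The change should be made, but it is not critical. The four endpoints are secondary, the study is descriptive with no hypothesis, and the sample-size reasoning for the primary endpoint is unaffected.

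**What to change.** 1. In Table 2, change the time point for serum potassium, serum creatinine, urine protein and blood pressure to "Baseline until end of observation period".
2. In Section 9.5.2 and the synopsis, define endpoints 9 to 12 as change from baseline, as defined in Section 3, to the last result in the observation period. State what happens when a patient has no baseline result.
3. Reword Section 9.1 so that baseline results from up to 12 months before the index event may be collected.
4. Separately, bring the index-event wording in Sections 3, 9.1, 9.2.1 and the synopsis into line. Add one field for any RAASi prescription on record before the index date, and report those patients separately. Eligibility need not change; a no-prior-use requirement could mean rescreening.

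The cost is one extra result per variable and one field per patient, from records in which the collector already looks back for eGFR, plus a protocol amendment. Two limits remain. A baseline result may be up to 12 months old. Because primary care data are seen only where they appear in hospital records (Section 9.4), a blank prior-use field would not prove new use.
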